## Figure 1 Study Flow Diagram

cCRT = concurrent chemoradiotherapy; ECOG PS = Eastern Cooperative Oncology Group Performance Status; NSCLC = non-small cell lung cancer.

Treatment arms may be opened sequentially or in parallel. Randomization will be stratified by histology (adenocarcinoma vs non-adenocarcinoma).

Enrollment to combination experimental arms may be stopped if planned interim analysis shows safety concerns or lack of efficacy. New combination experimental arms may be added based on emerging nonclinical and clinical data via a protocol amendment.

[figure not shown]
### 3.1.2 Treatment Regimen

Subjects will be randomized to a treatment arm and may remain on study treatment for up to 12 months. Study treatment will be discontinued upon disease progression, unacceptable toxicity, or other reason. See Section 4.1.6 for information on discontinuation of study drug for individual subjects.

#### 3.1.2.1 Durvalumab Control Arm

[Figure 2](#) presents the treatment regimen for the durvalumab monotherapy control arm.

## Figure 2 Treatment Regimen for Control Arm - Durvalumab Monotherapy

[figure not shown]
D = durvalumab; IV = intravenous; Q4W = every 4 weeks.

a Subjects in the control arm will receive durvalumab 1500 mg IV Q4W on Day 1 of each cycle.

#### 3.1.2.2 Experimental Arm A – Durvalumab Plus Oleclumab

Subjects randomized to Arm A will receive durvalumab in combination with oleclumab as presented in [Figure 3](#).

### Figure 3 Treatment Regimen for Arm A - Durvalumab Plus Oleclumab

[figure not shown]
D = durvalumab; IV = intravenous; O = oleclumab; Q2W = every 2 weeks; Q4W = every 4 weeks.

a Subjects in Arm A will receive durvalumab 1500 mg IV Q4W on Day 1 of each cycle, and oleclumab 3000 mg IV Q2W (Day 1 and Day 15) for Cycle 1 and Cycle 2 then Q4W starting on Cycle 3, Day 1. On days when both durvalumab and oleclumab are administered, oleclumab will be administered first.

#### 3.1.2.3 Experimental Arm B – Durvalumab Plus Monalizumab

Subjects randomized to Arm B will receive durvalumab in combination with monalizumab as presented in [Figure 4](#).

### Figure 4 Treatment Regimen for Arm B – Durvalumab Plus Monalizumab

D = durvalumab; IV = intravenous; M = monalizumab; Q2W = every 2 weeks; Q4W = every 4 weeks.

a Subjects in Arm B will receive durvalumab 1500 mg IV Q4W on Day 1 of each cycle, and monalizumab 750 mg IV Q2W on Days 1 and 15 of each cycle. On days when both durvalumab and monalizumab are administered, durvalumab will be administered first.

#### 3.1.3 Management of Study Medication Related Toxicities

The following general guidance should be followed for management of toxicities.

- 1 Next cycle administration can be delayed or discontinued
- 2 In the absence of clear alternative etiology, all events should be considered potentially immune mediated
- 3 In the event that an AE is considered related only to durvalumab or the combination novel therapy, both agents must be delayed

If unsure how to manage a subject, please contact the study medical monitor to discuss individual cases. Treatment for toxicities should be initiated prior to discussion with the study medical monitor.

Dose modifications are not allowed.

Guidelines for the management of immune-mediated reactions, infusion-related reactions, and non-immune-mediated reactions for durvalumab alone or in combination with the novel

immunotherapies are provided in the Toxicity Management Guidelines. These guidelines have been prepared by the sponsor to assist the investigator in the exercise of his/her clinical judgment in treating these types of toxicities. Following the guidelines is expected, but changes due to local site procedures are allowed according to the physician's judgement.

The most current version of the Toxicity Management Guidelines is to be maintained within the Site Master File.

### **3.1.4 Safety Review Committee**

An SRC will conduct safety reviews of all enrolled subjects at least twice a year. The SRC may make recommendations regarding continuation, modification, or termination of any study arm for safety concerns. They may request additional data (eg, clinical efficacy) as needed. Additional safety reviews may be conducted at the discretion of the SRC.

An SRC will consist of the following:

- The sponsor study Medical Monitor, or delegate
- Global Safety Physician, or delegate
- Study Statistician
- Principal Investigators, or delegates, from a subset of active investigational sites. The number of sponsor representatives will not exceed the number of Principal Investigators.
- External physician not associated with the conduct of the study (SRC Chairperson)

The Clinical Pharmacology Scientist, Patient Safety Scientist, Clinical Operations Representative, and other delegates may also be invited as appropriate. Other internal and external experts may be consulted by the SRC as necessary. The membership, roles, responsibilities, and details on the process flow/communication plan are provided in the SRC Charter.

## **3.2 Rationale for Dose, Population, and Endpoints**

### **3.2.1 Dose Rationale**

#### **3.2.1.1 Durvalumab**

Based on available PK and safety data for weight-based doses of durvalumab 10 mg/kg Q2W and 20 mg/kg Q4W and simulated PK data for a fixed dose of durvalumab 1500 mg Q4W, the fixed-dose regimen was predicted to provide comparable exposure to the body weight-based dosing regimens. Durvalumab has a flat exposure-response (efficacy and safety) relationship. Based on all the observed and simulated data, a fixed dosing regimen of 1500 mg Q4W was predicted to provide similar efficacy and safety profiles as the body weight-based dosing regimens. As detailed in the durvalumab IB, a fixed dose of 1500 mg Q4W is being used in

numerous ongoing studies. Therefore, a fixed dosing regimen of 1500 mg Q4W was selected in this study.

For additional details on the nonclinical and clinical data that informed durvalumab dose selection, see the durvalumab IB.

### **3.2.1.2 Oleclumab**

The oleclumab regimen of 3000 mg Q2W  $\times$  4 doses and then Q4W was selected based on data from the Phase 1 Study D6070C00001. In that study, oleclumab doses of 5, 10, 20, and 40 mg/kg Q2W were examined both as a monotherapy and in combination with durvalumab 10 mg/kg Q2W. Oleclumab was well tolerated and there were no observed DLTs either as monotherapy or in combination with durvalumab. Additionally, both oleclumab and durvalumab exposures in combination were comparable to monotherapy exposures. The oleclumab 40 mg/kg Q2W dose was selected for evaluation with durvalumab 10 mg/kg Q2W in the dose-expansion phase of that study.

A fixed dose of oleclumab 3000 mg Q2W  $\times$  4 doses is currently being explored based on simulations that oleclumab might achieve similar exposures to those observed with the 40 mg/kg Q2W dose schedule. The subsequent Q4W schedule at 3000 mg is predicted to result in adequate long-term exposures with median trough concentration above the estimated CD73 saturating concentration of approximately 40  $\mu$ g/mL (100-fold of estimated Michaelis-Menten constant from the population PK model) to maintain optimal CD73 saturation at steady state.

### **3.2.1.3 Monalizumab**

The monalizumab dose of 750 mg Q2W was selected based on the available clinical safety, tolerability, efficacy, and PK data from the ongoing Phase 1 Study D419NC00001. In that study, monalizumab doses of 22.5, 75, 225, and 750 mg Q2W and 750 mg Q4W were examined in combination with durvalumab 1500 mg Q4W. Monalizumab was well tolerated in all dose-escalation cohorts, and no DLTs were observed. The monalizumab 750 mg Q2W dose was identified for evaluation with durvalumab 1500 mg Q4W in the dose-expansion phase of the study.

## **3.2.2 Rationale for Study Population**

Patients with unresectable, Stage III NSCLC who have not progressed after cCRT will be considered for enrollment into the study. These characteristics defined the patient population in the Phase 3 PACIFIC study that showed superiority of durvalumab maintenance over placebo (see Section 1.5). Aligning with the PACIFIC target population provides support for use of a durvalumab control arm as the comparator for evaluating novel durvalumab combinations.

### **3.2.3 Rationale for Endpoints**

The primary objective of this platform study is to compare the clinical activity of durvalumab alone vs durvalumab in combination with novel agents. The overall study goal is early identification of novel durvalumab combinations that are more active than durvalumab alone in the treatment of patients with unresectable, Stage III NSCLC who have not progressed after cCRT. The classical efficacy endpoints of PFS and OS require long evaluation periods, eg, the ongoing PACIFIC study showed an interim median PFS of 17.2 months following a 3-year follow-up ([Antonia et al, 2018](#)). The current study will use objective response (OR) per Response Evaluation Criteria for Solid Tumors version 1.1 (RECIST v1.1), which is a widespread outcome measure in Phase 1-2 studies, as the primary endpoint to provide an earlier measure of antitumor activity. A difference in ORR between the durvalumab monotherapy arm and the novel combinations arms is believed to be clinically meaningful as responses to immunotherapies can be sustained over time and might relate to the overall PFS benefit. Clinical activity will be further assessed by secondary endpoints routinely used in oncology studies, including duration of response (DoR), DC, PFS-12, and PFS based on RECIST v1.1, and OS.

The safety and tolerability of each study treatment will be assessed by the standard safety endpoints, including AEs, SAEs, laboratory parameters, vital signs, and other standard clinical parameters.

## **4 MATERIALS AND METHODS**

### **4.1 Subjects**

#### **4.1.1 Number of Subjects**

Up to approximately 60 subjects per experimental treatment arm will be randomized with equal ratios to durvalumab control and each of the open experimental arms. New durvalumab combination experimental arms may be added over time following protocol-specific guidelines (see Section [1.6.3](#)) and therefore the total number of subjects randomized to the durvalumab control arm might be higher than 60 subjects. Details regarding the specifics of a new combination arm will be provided via protocol amendment. See also Section [4.6.1](#) for potential changes to the randomization scheme and changes to overall study enrollment in the control arm and the combination experimental arms during the study.

#### **4.1.2 Inclusion Criteria**

Subjects must meet all of the following criteria:

- 1 Written informed consent and any locally required authorization obtained from the subject prior to performing any protocol-related procedures, including screening evaluation
- 2 Age 18 years or older

- 3 Body weight  $\geq 35$  kg
- 4 Subjects must have histologically or cytologically documented NSCLC who present with locally advanced, unresectable, Stage III disease
- 5 Subjects must have completed, without progressing, definitive cCRT within 42 days prior to being randomized into the study:
  - Definitive radiotherapy refers to a total dose  $\geq 60$  Gy at 1.8 Gy per fraction or bioequivalent dose
  - Concurrent chemotherapy refers to a platinum-based doublet
  - The final chemotherapy administration must end prior to, or concurrently with, the final dose of radiation
- 6 Subjects must have at least one previously irradiated tumor lesion that can be measured by RECIST v1.1 (RECIST v1.1 guidelines permit previously irradiated lesions to be considered measurable if defined in the protocol [see Section 3.1.3 in [Eisenhauer et al, 2009](#)])
- 7 Provision of tumor tissue sample, when available, from original diagnosis obtained before initiation of chemoradiotherapy (tumor tissue block or unstained slides are acceptable; refer to Laboratory Manual for details)
- 8 Life expectancy  $\geq 12$  weeks
- 9 Eastern Cooperative Oncology Group (ECOG) Performance Status of 0 or 1
- 10 Adequate organ and marrow function as defined in [Table 4](#):

**Table 4 Criteria for Adequate Organ and Marrow Function**

| Parameter     |   | Value  |
|---------------|---|--|
| Hematological | Hemoglobin a                         | $\geq 9.0$ g/dL (5.59 mmol/L)                              |
|               | Absolute neutrophil count a          | $\geq 1.0 \times 10^9$ /L (1000 per mm  )      |
|               | Platelet count a                     | $\geq 100 \times 10^9$ /L (100,000 per mm  )   |
| Hepatic       | Total bilirubin                                 | $\leq 1.5 \times$ ULN in the absence of Gilbert's syndrome |
|               |   | $\leq 3 \times$ ULN if the patient has Gilbert's syndrome  |
|               | Alanine transaminase and aspartate transaminase | $\leq 2.5 \times$ ULN                                      |
| Renal         | Calculated creatinine clearance b    | $\geq 40$ mL/minute  |

ULN = upper limit normal.

a Hematological criteria cannot be met with ongoing or recent blood transfusions (within 14 days prior to the scheduled first dose of study treatment) or require growth factor support (within 21 days prior to the scheduled first dose of study treatment).

b As determined by Cockcroft-Gault (using actual body weight; [Cockcroft and Gault, 1976](#)) or 24-hour urine creatinine clearance.

- 11 Females of childbearing potential and non-sterilized male subjects with female partners of childbearing potential must use effective methods of contraception from screening to 180 days after the final dose of study treatment (see [Appendix A](#))

#### 4.1.3 Exclusion Criteria

Any of the following would exclude the subject from participation in the study:

- 1 Involvement in the planning and/or conduct of the study (applies to both sponsor staff and/or staff at the study site)
- 2 Concurrent enrollment in another clinical study, unless it is an observational (non-interventional) clinical study or during the follow-up period of an interventional study
- 3 Mixed small cell and non-small cell lung cancer histology
- 4 Current or prior use of immunosuppressive medication within 14 days before the first dose of study drug. The following are exceptions to this criterion:
  - Intranasal, inhaled, topical steroids, or local steroid injections (eg, intra-articular injection)
  - Systemic corticosteroids at physiologic doses not to exceed 10 mg/day of prednisone or its equivalent
  - Steroids as premedication for hypersensitivity reactions (eg, CT scan premedication)
- 5 Prior exposure to any anti-PD-1, anti-PD-L1, or anti-cytotoxic T-lymphocyte-associated antigen-4 (CTLA-4) antibody for the treatment of NSCLC
- 6 Any unresolved toxicity National Cancer Institute Common Terminology Criteria for Adverse Events version 5.0 (NCI CTCAE v5.0) > Grade 2 from the prior chemoradiation therapy
- 7 Subjects with history of  $\geq$  Grade 2 pneumonitis from prior chemoradiation therapy
- 8 Subjects with a history of venous thrombosis within the past 3 months.
- 9 Subjects with history of myocardial infarction, transient ischemic attack, or stroke in the past 6 months.
- 10 Congestive heart failure  $\geq$  Class 3 based on New York Heart Association Functional Classification
- 11 Major surgical procedure (as defined by the investigator) within 28 days prior to the first dose of study drug
- 12 Active or prior documented autoimmune or inflammatory disorders (including inflammatory bowel disease [eg, colitis or Crohn's disease], diverticulitis [with the exception of diverticulosis], systemic lupus erythematosus, Sarcoidosis syndrome, or Wegener syndrome [granulomatosis with polyangiitis, Graves' disease, rheumatoid arthritis, hypophysitis, uveitis, etc]). The following are exceptions to this criterion:
  - Subjects with vitiligo or alopecia
  - Subjects with hypothyroidism (eg, following Hashimoto syndrome) stable on hormone replacement
  - Any chronic skin condition that does not require systemic therapy
  - Subjects with celiac disease controlled by diet alone
- 13 History of active primary immunodeficiency

- 14 Active infection including tuberculosis, hepatitis B, hepatitis C, or human immunodeficiency virus (HIV)
- 15 History of allogenic organ transplantation
- 16 Known allergy or hypersensitivity to study drug formulation(s)
- 17 QTcF interval  $\geq$  470 ms
- 18 Uncontrolled intercurrent illness, including but not limited to, ongoing or active infection, symptomatic congestive heart failure, uncontrolled hypertension, unstable angina pectoris, cardiac arrhythmia, interstitial lung disease, serious chronic gastrointestinal conditions associated with diarrhea, or psychiatric illness/social situations that would limit compliance with study requirement, substantially increase risk of incurring AEs or compromise the ability of the patient to give written informed consent
- 19 Receipt of live attenuated vaccination within 30 days prior to study entry
- 20 History of another primary malignancy except for:
  - Malignancy treated with curative intent and with no known active disease  $\geq$  5 years before the first dose of study drug and of low potential risk for recurrence
  - Adequately treated non-melanoma skin cancer or lentigo maligna without evidence of disease
  - Adequately treated carcinoma in situ without evidence of disease
- 21 Females who are pregnant, lactating, or intend to become pregnant during their participation in the study

#### **4.1.4 Subject Enrollment and Randomization**

Study participation begins (ie, a subject is “enrolled”) once written informed consent is obtained. Once informed consent is obtained, a subject identification (SID) number will be assigned by a central system (ie, an interactive voice/web response system [IXRS]), and the screening evaluations may begin to assess study eligibility (inclusion/exclusion) criteria. The SID number will be used to identify the subject during the screening process and throughout study participation, if applicable.

A master log of all consented subjects will be maintained at the site and will document all screening failures (ie, subjects who are consented but do not meet study eligibility criteria and are not randomized), including the reason(s) for screening failure.

Subjects who fail to meet the inclusion/exclusion criteria (ie, screening failures) should not be randomized or receive study treatment. Further details regarding randomization are detailed in Section 4.6.1.

#### **4.1.5 Withdrawal from the Study**

Subjects are free to withdraw their consent to participate in the study (study treatment and assessments) at any time, without prejudice to further treatment. All study drug(s) should be

returned by the subject. If a subject withdraws from further participation in the study, then no further study visits or data collection should take place.

#### **4.1.6 Discontinuation of Investigational Product**

An individual subject in any of the treatment arms will not receive any further study drug if any of the following occur in the subject in question:

- 1 Withdrawal of consent
- 2 Any toxicity/AE that in the opinion of the investigator and/or the sponsor, warrants discontinuation of further dosing
- 3 Any AE that meets criteria for discontinuation as defined in the Toxicity Management Guidelines (see Section [3.1.3](#))
- 4 Pregnancy or intent to become pregnant (Section [5.6.2](#))
- 5 Delay of more than 56 days from the last administration of study drug to the next planned dose
- 6 Confirmation of disease progression (Section [4.3.1](#))
- 7 Unconfirmed disease progression and investigator determination that the subject is not eligible for a confirmation scan (Section [4.3.1](#))
- 8 Initiation of alternative anticancer therapy
- 9 Intercurrent illness or medical condition, in the judgment of the investigator and/or the sponsor warrants discontinuation of further dosing

Subjects who are permanently discontinued from receiving study treatment will be followed for protocol-specified assessments, including follow-up of any AEs, unless consent is withdrawn from further study participation (Section [4.1.5](#)), disease progression, the subject starts alternative treatment/clinical study, or the subject is lost to follow-up. All subjects will be followed for survival until the end of the study unless consent is withdrawn from further study participation.

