### **3 STUDY DESIGN**

#### **3.1 Description of the Study**

##### **3.1.1 Overview**

COAST is a Phase 2, open-label, multicenter, randomized, multidrug platform study of durvalumab alone or in combination with novel agents in subjects with locally advanced, unresectable, Stage III NSCLC.

[figure not shown]
The study will evaluate the clinical activity and safety of durvalumab alone or in combination with novel agents in subjects with Stage III NSCLC who have not progressed following definitive cCRT ([Figure 1](#)). Subjects will be randomized into the study and initiate study treatment within 42 days from the last session of cCRT. Information on subject randomization and sample size is provided in [Section 4.6.1](#) and [Section 4.8.2](#), respectively. Up to approximately 80 sites globally will participate in this study.

Subjects may be treated for up to 12 months. Study treatment will be discontinued upon disease progression, unacceptable toxicity, or other reason, eg, subject decision or noncompliance with study procedures. Overall, all subjects continuing in the study must adhere to the study procedures for up to 5 years (from randomization) provided they achieve disease control (DC) and remain disease free. Subjects who have experienced PD will be followed for survival.

All subjects will be followed for survival until the end of the study as per the time points shown in [Table 6](#). After completing the 5-year post-randomization study period, all subjects included into any treatment arm may be contacted annually for survival until 5 years after the final subject is randomized into the study or until the sponsor stops the study, whichever occurs first. The platform nature of the study allows an individual experimental arm to be permanently closed while the overall COAST study remains open.

New durvalumab combination experimental arms may be added based on emerging nonclinical and clinical data via protocol amendment (see [Section 1.6.3](#)). Interim futility analyses will be performed using Bayesian predictive probability (PP; see [Section 4.8.7](#)).

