#### 4.2.2 Follow-up Period

**Table 6** presents follow-up procedures for subjects who completed study treatment and maintain DC, subjects who discontinued study treatment due to other reason not related to PD (Section 4.1.6), and subjects who experienced unconfirmed PD and are eligible for a confirmation scan. Procedures for subjects who discontinue study treatment due to PD are provided in Section 4.2.3. Overall, all subjects continuing in the study must adhere to the study procedures for up to 5 years (from randomization) provided they achieve DC and remain disease free.

As OS is a late endpoint in this patient population, after the planned 5-year post randomization study period, subjects may be contacted for survival every 12 months.

**Table 6 Schedule of Follow-up Procedures: Subjects Who Completed Study Treatment and Maintain DC, Subjects Who Discontinued Study Treatment Due to Other Reason Not Related to PD, and Subjects Who Experienced Unconfirmed PD and are Eligible for a Confirmation Scan**

| Time since Cycle 1 Day 1                    | ≤ 12 Months                          | > 12 to ≤ 24 Months               | > 24 to 60 Months             |
|---|--------------------------------------|-----------------------------------|-------------------------------|
| Follow-up based on previous scheduled visit | Every 8 Weeks
(± 3 days)          | Every 12 Weeks
(± 7 days)      | Every 6 Months
(± 4 weeks) |
| Procedure                            |                                      |                                   |                               |
| Physical examination                        | X                                    | X                                 | X                             |
| Vital signs                                 | X                                    | X                                 | X                             |
| ECOG performance status                     | X                                    | X                                 | X                             |
| Serum chemistry                             | X                                    | X                                 | X                             |
| Thyroid function tests a         | X                                    | X                                 | X                             |

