#### **4.5.1.6 Treatment Administration**

The first day of dosing is considered Day 1.

No specific premedication is required for durvalumab, oleclumab, or monalizumab. Details of any premedication or concomitant medication given to manage or prevent AEs should be recorded on the electronic case report form (eCRF).

A physician must be present at the site or immediately available to respond to emergencies during all administrations of investigational product. Fully functional resuscitation facilities should be available.

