## 4.8 Statistical Evaluation

### 4.8.1 General Considerations

Tabular summaries will be presented by treatment group. Categorical data will be summarized by the number and percentage of subjects in each category. Continuous variables will be summarized by descriptive statistics. Additional details of statistical analyses will be described in the statistical analysis plan.

The Intent-to-treat (ITT) Population includes all subjects who are randomized. Subjects will be analyzed according to their randomized treatment group.

The As-treated Population includes all subjects who receive any investigational product. Subjects will be analyzed according to the treatment they actually receive.

The Response-evaluable Population includes subjects from the As-treated Population who have a baseline disease assessment, have the opportunity to be followed for at least 16 weeks at the time of the DCO (ie, dosed at least 16 weeks prior to the time of the DCO), and either has at least one post-baseline disease assessment and/or discontinued treatment due to death or disease progression.

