### 3 STATISTICAL METHODS

#### 3.1 General Considerations

Tabular summaries will be presented by treatment group. Categorical data will be summarized by frequency distribution (number and percentage of subjects falling within each category). Continuous variables will be summarized by descriptive statistics including N, mean, standard deviation, median, and range (minimum and maximum). All available data will be used, and thus missing data will not be imputed, unless otherwise specified. In general, subjects with missing data for a parameter will be excluded from the summary of this parameter. Tables will be supported by data listings showing the original data forming the basis for the summaries. Data listings will be sorted by treatment group, subject number and date collected where applicable.

Unless stated otherwise, two-sided confidence intervals will be produced at 95%. Baseline values will be defined as the last valid assessment prior to the first administration of IP. Assessments on the day of the first dose where neither time nor a nominal pre-dose indicator are captured are considered prior to the first dose if such procedures are required by the protocol to be conducted before the first dose.

Data analyses will be conducted using the SAS® System (SAS Institute, Inc., Cary, NC, USA) Version 9.4 or above, unless otherwise specified. All analysis outputs will be validated according to MedImmune SAS programming standards and MedImmune validation procedures.

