**Table 3.4.1      Summary of Censoring Guidelines for PFS**

Situation	Date of PD/Death or Censoring	PFS Outcome
Documented Progressive Disease (PD) or death	Date of earliest sign of PD or death, whichever comes first	Event (unless the censoring rule specified below)
Death or PD immediately after $\geq 2$ consecutive missed or non-evaluable disease assessments as per the protocol specified assessment schedule	Date of last progression-free disease assessment prior to missed or non-evaluable assessments, or randomization, whichever occurred last	Censored
No PD or death at time of analysis or lost to follow-up	Date of last evaluable progression-free disease assessment	Censored
No tumor assessment at baseline and no evidence of PD at first post-baseline disease assessment OR No tumor assessment post-first dose, and no death prior to second scheduled post-baseline disease assessment	Date of randomization	Censored

PD = progressive disease; PFS = progression-free survival.

Subjects having missing lesion data at baseline or no disease assessments post-first dose of IP will have PFS censored at the date of randomization unless the subject dies prior to the second scheduled post-baseline disease assessment in which case the death date will qualify as a PFS event.

If a subject has two or more consecutive completely missed or non-evaluable assessments followed immediately by death or an assessment showing radiologic disease progression, then the subject will be censored for PFS. PFS will be censored at the date of randomization or the last progression-free disease assessment prior to the missed or non-evaluable assessments, whichever occurred last.

If a subject has two or more consecutively missed or non-evaluable assessments followed by an assessment showing no radiologic disease progression, then the assumption will be that the subject did not progress during the missed or non-evaluable assessments.

The length of gap (in number of days) to determine two or more consecutive assessments is defined as the following:

- 126 days during the first 12 months (A 8-week disease assessment interval plus a 7-day window for each assessment).

- 182 days from month 12 to month 24 (A 12-week disease assessment interval plus a 7-day window for each assessment).
- 422 days after month 24 (A 6-month disease assessment interval plus a 4-week window for each assessment).

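### Efficacy runs from randomisation, but the SAP baseline, the PFS censoring rule and the scan schedule start at first dose, so a never-dosed subject's progression is discarded

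*Protocol*

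**What the plan says.** **Population and clock.** Protocol 4.8.1: "The Intent-to-treat (ITT) Population includes all subjects who are randomized". PFS starts at randomisation in both documents (Protocol 4.8.3, SAP 3.4.2.4), and so does OS (SAP 3.4.2.5). Subjects are not replaced (Protocol 4.1.7).

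**Scan schedule.** Protocol 4.5.1.6: "The first day of dosing is considered Day 1". Table 5 is laid out by dosing cycle and Table 6 by time since Cycle 1 Day 1. Protocol 4.2.2 describes Table 6 as giving "follow-up procedures for subjects who completed study treatment and maintain DC, subjects who discontinued study treatment due to other reason" other than progression, plus subjects with unconfirmed progression who can have a confirmation scan. Protocol 4.1.6 adds: "Subjects who are permanently discontinued from receiving study treatment will be followed for protocol-specified assessments". None of these names a subject who was randomised and never dosed.

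**Baseline.** SAP 3.1: "Baseline values will be defined as the last valid assessment prior to the first administration of IP".

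**PFS censoring.** The text under SAP Table 3.4.1 says that subjects with "no disease assessments post-first dose of IP will have PFS censored at the date of randomization", unless they die before the second scheduled post-baseline assessment.

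**Response.** SAP 3.4.1.1 counts missing response as non-response. SAP 3.4.2.1 makes best overall response non-evaluable when baseline lesion data are missing.

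**The 42-day window.** Protocol 3.1.1 has subjects randomised and then "initiate study treatment within 42 days from the last session of cCRT"; the synopsis and SAP 2.2 agree. Inclusion criterion 5 (4.1.2) requires "definitive cCRT within 42 days prior to being randomized into the study", and 4.6.1 allows a further 3 days from assignment to dosing.

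**The concern.** The analysis set and the time origin belong to randomisation, while the rules that generate and classify outcomes belong to first dose. For dosed subjects the gap is at most a few days. For a subject who is never dosed there is no first dose, so there is no defined baseline, no scheduled scan, and no assessment that can meet the post-dose condition.

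The study is open label (Protocol 4.6.2) and the control drug is the standard of care (Protocol 1.5), so some subjects may decline after learning their allocation. If such subjects occur, the SAP removes their follow-up from PFS by rule even when it was observed. An ITT analysis should not do that.

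**Working it through.** **1. One never-dosed subject under the two PFS rules.** Row 1 of SAP Table 3.4.1 (progression or death is an event) yields to the censoring rows below it. Such a subject can never have a post-dose assessment, so the last row applies.

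| What is observed | Protocol 4.8.3 | SAP Table 3.4.1, read literally |
|---|---|---|
| A scan shows progression; no early death | Event | Censored at randomisation |
| Early death | Event | Event |
| Later death | Event | Censored at randomisation |
| Alive, last scan progression-free | Censored at that scan | Censored at randomisation |

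Early means before the second scheduled post-baseline assessment. In Table 5 that is Cycle 5, or 4 x 28 = 112 days after first dose, so for a never-dosed subject this window has no date either.

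**2. Effect on PFS.** With the SAP formula, censoring at randomisation gives (0 + 1)/(365.25/12) = 1/30.4375 = 0.033 months. The subject contributes essentially no time at risk. Unequal numbers censored this way lose information but do not by themselves shift the hazard ratio. Bias arises if the subjects removed differ in prognosis between arms. The early-death exception adds an outcome-dependent element, because deaths are kept and progressions are not. The documents give nothing from which to size either.

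**3. Reproducing the plan's ORR precision.** Inverting exact unconditional one-sided 2.5% tests on the raw difference, n = 60 per arm and 18 control responders:

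| Experimental responders | Recomputed 95% CI | Protocol Table 9 / SAP Table 2.4-1 |
|---|---|---|
| 24 | -8.7% to 28.2% | -9% to 28% |
| 27 | -3.7% to 32.9% | -4% to 33% |
| 30 | 1.3% to 37.7% | 1% to 38% |
| 33 | 6.4% to 42.3% | 6% to 42% |

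All four rows agree after rounding.

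**4. Effect on ORR.** Let k be the excess of never-dosed controls out of 60. The documents give no rate, so k is an assumption. With a true ORR of 30% in both arms, control ORR becomes 30% x (60 - k)/60 and the difference shifts by 30% x k/60. The last column is exact enumeration with an unstratified Pearson chi-square at two-sided 0.05, standing in for the stratified CMH test.

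| k | Control ORR | Shift | Chance of nominal significance favouring experimental |
|---|---|---|---|
| 0 | 30.0% | 0 | 2.6% |
| 1 | 29.5% | 0.5 points | 3.0% |
| 3 | 28.5% | 1.5 points | 3.9% |
| 6 | 27.0% | 3.0 points | 5.6% |

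Refusals in an experimental arm act the other way: at 50% true ORR, 3 of 60 give 50% x 57/60 = 47.5%.

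**5. How much of this better-timed scans could recover.** Responses count only before subsequent anticancer treatment (SAP 3.4.1.1), and withdrawal from the study ends data collection (Protocol 4.1.5). That leaves never-dosed subjects who stay in the study without other therapy. If they respond at the 16.0% placebo rate quoted in Protocol 1.5 (an assumption), recovery is 16.0%/60 = 0.27 points per subject, or 0.8 points for three.

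**6. The 42-day statements.** Randomisation on day 42 is allowed by 4.1.2, and 4.6.1 then allows dosing to day 42 + 3 = 45. Protocol 3.1.1, the synopsis and SAP 2.2 have treatment start by day 42. These cannot all hold.

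**The case against.** The strongest reply is that the plan works for these subjects in practice. A post-cCRT screening scan is required (Protocol Table 5, footnote h). SAP 3.3.2 summarises baseline tumour characteristics for the whole ITT population. Protocol 3.1.1 and 4.2.2 hold continuing subjects to procedures for up to 5 years from randomisation, and 4.1.6 follows all subjects for survival. Counting missing response as non-response is a conventional, explicit ITT rule. SAP 3.3.1 already reports disposition. With dosing due within 3 days of assignment, never-dosed subjects should be few.

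Much of this stands. The ORR rule is not a defect, the scan usually exists, and the effect is probably small. It does not rescue the SAP wording: the baseline definition does not reach that scan for a never-dosed subject, the general follow-up duty gives no timetable, and the censoring rule discards progression that was observed.

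Three stronger readings are tempting, and the documents do not support them:
- A reader might infer that unequal open-label refusals alone bias PFS. Censoring at randomisation does not do so without a difference in prognosis (step 2).
- A reader might infer that one lost control responder could tip the interval past zero and that better scan follow-up would prevent it. By the same exact method, 29 vs 18 of 60 gives -0.4% to 36.1%, and 29 vs 17 gives 1.3% to 37.7%. But a control who withdraws or is treated elsewhere stays a non-responder after any change in scan timing. The study is also explicitly not sized for a hypothesis test (Protocol 4.8.2).
- A reader might infer that the 42-day conflict creates never-dosed subjects. It makes a subject late, not undosed: 4.6.1 requires only that the monitor be told of a delay, and under SAP 3.3.5 deviations do not remove subjects from analysis populations unless otherwise specified.

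**Conclusion.** The point holds for the anchoring rules. Read literally, SAP 3.1 leaves a randomised, never-dosed subject without a baseline. SAP 3.4.2.4 with Table 3.4.1 discards that subject's documented progression while keeping an early death, contrary to ITT and to the PFS definition in Protocol 4.8.3. The possible PFS bias cannot be sized and depends on a prognostic difference between the never-dosed subjects of the two arms.

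For ORR the consequence follows from the stated non-responder rule. It is about 0.5 points per excess never-dosed control at an assumed 30% ORR, against a CI half-width of about 18 points, and only a minor part could be recovered. The correction is worth making because the rule gives a wrong ITT result and costs almost nothing to change. The 42-day contradiction is a separate matter.

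**What to change.** - **SAP 3.1:** define efficacy baseline as the last valid assessment before first dose or, for a subject never dosed, on or before randomisation.
- **SAP 3.4.2.4 and Table 3.4.1:** replace the post-first-dose condition by a post-randomisation one, in both the table and the text beneath it.
- **SAP 3.3.1:** report the number of randomised, never-dosed subjects and the reasons, by arm.
- **Protocol 4.2.2 and Table 6, for any future arm:** cover randomised, never-dosed subjects who remain in the study, with visits timed from randomisation. Protocol 9.1 states that all current subjects have finished treatment, so this does not help the existing arms.
- **Separately:** reconcile the 42-day statements in Protocol 3.1.1, the synopsis and SAP 2.2 with Protocol 4.1.2 and 4.6.1.

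The SAP items cost wording and one disposition summary. The protocol item would add standard scans for the few undosed subjects who agree to stay in follow-up.
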